In Malawi, all pregnant women presenting for care receive opt-out HIV testing at their first antenatal care visit. Women who test HIV+ undergo adherence counseling and start ART the same day. PND screening and assessment are rare to nonexistent at antenatal/ART clinics in Lilongwe, as in most clinical settings in Malawi.

UNC Project in Lilongwe will serve as the administrative home for the study and has longstanding relationships with Bwaila FHU, antenatal/ART clinics in Lilongwe, and the Ministry of Health.

F4. Study Population:

Women (92 total): As of this protocol v3.2, we have recruited a total of 12 women from our original 3 clinics. As we launch activities at our two new clinics and reduce to 2 arms, we will seek to recruit 40 new participants per arm or 80 new participants total, for a total enrollment of 92 participants. All 92 women will contribute to analyses of feasibility and acceptability, but only the new 80 women will contribute to between-arm comparisons due to the differences in sites.

We will include 92 HIV-infected, depressed women initiating, re-initiating, or continuing ART who engage in ANC and are identified with antenatal depression at ≤ 34 weeks gestation to allow sufficient time for approximately 4 prenatal counseling sessions and approximately 2 postnatal counseling sessions. Women with a score ≥ 10 on the EPDS^{48,49} and/or ≥ 8 on the SRQ-20 will be considered to be depressed and will be invited to participate.

Inclusion criteria:

- HIV-infected, pregnant women initiating, re-initiating, or continuing ART during antenatal care (ANC)
- ≤ 34 weeks gestation to allow sufficient time for approximately 4 prenatal counseling sessions and approximately 2 postnatal counseling sessions.

- Screened positive for depression with a score ≥ 8 on the SRQ-20
- At least 18 years of age

Feasibility of recruitment – Approximately 30 HIV-infected women initiate or re-initiate ART monthly at each of the study sites, or 150 women over 6 months, with ~90% presenting at ≤ 30 weeks. Based on our group's systematic review³⁴, we conservatively estimate 30% of HIV-infected women will have antenatal depression, suggesting that enrolling ~6 women per site per month is feasible. Utilization of two additional clinics will aid in timely participant recruitment should enrollment at the three primary sites lag behind expected targets.

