Psychosocial counselors (n=4 total): Trained psychosocial counselors will be identified to administer counseling sessions for both the AFB and EFB arm. We will recruit 2 female counselors for each primary intervention arm clinic to complete up to 4 individual prenatal counseling sessions and up to 2 postnatal group sessions (approximately 100 counseling sessions per counselor total over 4-6 months, and ~ 20 counseling sessions per counselor per month). Group counseling will be offered on multiple days; each group will have 5-8 women attending 2 sessions.

Research Assistants (n=3): Trained research assistants will be hired to conduct participant screening and to complete baseline and 6-month data collection with all participants at each of the five study clinics. Research assistants will spend the majority of their time in each of the three primary study sites and rotate between the remaining two clinics as needed.

Supervisors (n=2): Supervision for counselor will be provided by the study mental health professionals (n=2).

F6. Pilot Trial Arms

We have adapted the Friendship Bench intervention to meet the particular needs of HIV-infected women with PND and enhanced it to additionally support engagement in perinatal HIV care. We will conduct a pilot trial, comparing Enhanced Friendship Bench (EFB), to enhanced standard care (ESC).

1. Arm 1: Adapted Friendship Bench (AFB - DROPPED) – [Note: This arm is no longer included in the trial as of protocol v3.1, but this text is retained to aid with understanding Arm 2.] The existing Friendship Bench intervention protocol has been adapted to address the unique needs of HIV-infected women. AFB will include 4 individual prenatal counseling session (in-person or by phone) and 2 group postnatal counseling sessions. No specific retention support will be provided, but participants may identify barriers to engagement in HIV care to address during their pre- or postnatal counseling sessions.

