Composite outcome: Retained in HIV care, with improved depression: We will assess a combined outcome at 6 months of whether a woman attended an HIV visit within the last 30 days and achieved remission (defined as ≥50% improvement in SRQ-20 score from baseline and an SRQ score <8). We will compare the following additional outcomes at 6 months postpartum: Self-Reporting Questionnaire (SRQ-20): The proportion of women reporting a score >8; Retention in HIV Care: (a) The proportion of women who attended an HIV care visit in the last 30 days; (b) considering the increase in visit spacing during the COVID-19 pandemic, we will consider a second definition of retention in HIV care of at least 2 visits at least 30 days apart in the first 6 months postpartum; Viral Load Suppression: The proportion of women with a HIV RNA level <1000 copies/mL; Infant health: the proportion of women whose infants received an HIV RNA test.

F10. Statistical Analysis – Baseline mental health, HIV, and reproductive health characteristics of women will be compared across 2 study arms using t-tests for continuous variables and chi-square tests for categorical variables to assess balance across study arms. **Primary Outcomes** – Quantitative measures of feasibility, acceptability, and fidelity will be summarized using means and standard deviations or proportions and compared across arms using statistical models for continuous or binary outcomes, as appropriate. Specifically,

we will compare the mean number of women enrolled and the proportion of women retained in EFB or ESC through 6 months postpartum (feasibility); the proportion of participants who found the intervention easy to administer and helpful (acceptability), and the proportion of counseling sessions scoring either 'meeting expectations' or 'exceeding' expectations' on at least 80% of applicable checklist items (fidelity) across study arms. **Secondary Outcomes** will be analyzed as above at 6 months postpartum across 2 study arms. In addition, statistical models examining differences in SRQ-20 scores at 6 months will be generalized linear models.

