F11. Sample Size. The primary goal of this R34 proposal is to evaluate the feasibility, acceptability, and fidelity of the adapted and enhanced Friendship Bench intervention to improve PND and engagement in HIV care among HIV-infected women. In Aim 3, we will enroll 92 HIV-infected women with PND in a 2-arm pilot (n=12 total in the clinic-randomized phase, n=40 women per arm in the individually randomized phase) to compare enhanced standard care with the enhanced Friendship Bench intervention. Information on preliminary effectiveness of the intervention across a range of mental health and engagement in HIV care outcomes will be assessed, but interpreted cautiously as effectiveness is not the primary aim of this pilot study. Intervention effectiveness will subsequently be assessed in a large-scale clinic-randomized controlled trial. Given that the objective of this analysis is to estimate feasibility, acceptability, and fidelity of the described interventions, feasible sample sizes (n=40/arm; 92 including both the clinic-randomized and individually randomized phases) were determined according to clinic patient volumes and estimated perinatal depression among women living with HIV in the study setting. Precision estimates for the given sample size are based on two-tailed statistical significance tests and a Type 1 error probability (α) of 0.05. The sample of 92 women (40 per arm) will be sufficient to estimate quantitative measures of feasibility and acceptability with reasonable precision (e.g., confidence intervals around proportions of ± 5 -9 percentage points across all arms, and ± 9 -17 percentage points within a given arm). This margin of error was estimated using a desired sample size of 92 and population feasibility and acceptability proportions ranging from 10 to 50%.

E. Potential Challenges and Solutions

What if women are lost to follow-up (LTFU) between pre and postnatal care? Our proposal directly addresses the high rate of LTFU in the postnatal period^{2,52} for women on Option B+ by providing linkage to care coordination from the antenatal to ART clinic and measuring engagement in care through 6 months postpartum. The information gathered at the pilot stage will help to inform the design of a large-scale randomized controlled trial to improve PND and engagement in HIV care during the peripartum period.

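### F10 makes no allowance for EFB women sharing counselors and postnatal groups, so EFB intervals and EFB-versus-ESC standard errors are too small, by an amount the documents do not fix

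*Combined protocol and SAP*

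**What the plan says.** **Design.** The two new sites randomize individual women (F2). F11 plans "n=40 women per arm in the individually randomized phase", and F4 states that "only the new 80 women will contribute to between-arm comparisons due to the differences in sites".

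**Delivery.** EFB contains every element of AFB plus retention strategies (F6). A woman has about four individual sessions with a counselor, optional postnatal groups, and up to six home visits at which the counselor can deliver her medication. On staffing, F4 lists four counselors in total, planned for AFB and EFB together: "We will recruit 2 female counselors for each primary intervention arm clinic". On the groups: "each group will have 5-8 women attending 2 sessions". ESC women have no counseling sessions (F8).

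**Analysis.** In F10, feasibility, acceptability and fidelity are to be "compared across arms using statistical models for continuous or binary outcomes, as appropriate", and secondary outcomes are handled the same way. For SRQ-20 it adds: "In addition, statistical models examining differences in SRQ-20 scores at 6 months will be generalized linear models". The t-tests and chi-square tests in F10 are for baseline balance only.

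**Precision.** F11 states: "Precision estimates for the given sample size are based on two-tailed statistical significance tests and a Type 1 error probability (α) of 0.05". For proportions of 10-50% it prints margins of 5-9 points across all arms and 9-17 "percentage points within a given arm". No ICC, design effect, random effect or cluster-robust variance appears in any section.

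**The concern.** Women are randomized one by one, but those in EFB are then treated by a small number of people and, after birth, partly in groups. Women who share a counselor or a group tend to have more similar outcomes than women who do not. ESC has no counterpart to this, so the design is partially nested: clustered in one arm and not in the other.

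A generalized linear model with no counselor or group term treats all 80 women as independent. If the ICC is positive, the variance of the EFB mean or proportion is understated, and so is the standard error of each post-randomization EFB-versus-ESC comparison. Because counselors also make home visits and can bring medication, the effect may reach retention and viral suppression as well as SRQ-20. Retention by arm is one of the primary feasibility measures. The pilot is meant to inform a larger trial, so intervals that are too narrow would be carried forward. If counselor and group membership are not recorded during delivery, they may be hard to recover afterwards.

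**Working it through.** **Inputs.** 40 women per arm and two-sided alpha 0.05 (F11); proportions 0.10 to 0.50 (F11); groups of 5-8 (F4). Women per counselor, m: 40/4 = 10 if all four counselors in F4 deliver EFB, 40/2 = 20 if two do. *Assumptions:* ICC 0.01 to 0.10, equal caseloads, and no clustering in ESC.

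**Step 1: the plan's own figures.** Half-width = 1.96 × √(p(1−p)/n).

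- n = 40: 1.96 × √(0.09/40) = 9.3 points and 1.96 × √(0.25/40) = 15.5 points. F11 prints 9-17.
- n = 92: 6.1 and 10.2 points. F11 prints 5-9.
- Wilson intervals give 9.6-14.8 and 6.2-10.0. A continuity correction gives 10.6-16.7 and 6.7-10.8. Neither matches.
- The former sizes come closer: n = 35 gives 9.9-16.6 and n = 105 gives 5.7-9.6.

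The printed ranges do not reproduce at the current sizes and look carried over from 35 women per arm and 105 in total. No variant contains a clustering allowance.

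**Step 2: add EFB-only clustering.**

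- Design effect DE = 1 + (m − 1) × ICC in EFB, and 1 in ESC.
- EFB half-width is multiplied by √DE.
- Between-arm standard error (equal variances, 40 against 40) is multiplied by R = √((1 + DE)/2).
- True error of the unadjusted nominal 5% test = 2 × (1 − Φ(1.96/R)).

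Example, m = 10 and ICC 0.05: DE = 1 + 9 × 0.05 = 1.45; effective n = 40/1.45 = 27.6; R = √(2.45/2) = 1.107; true error about 7.7%.

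| EFB cluster | ICC | DE | EFB half-width, p = 0.10 / 0.50 | R | True error |
|---|---|---|---|---|---|
| Counselor, m = 10 | 0.01 | 1.09 | 9.7 / 16.2 | 1.022 | 5.5% |
| | 0.05 | 1.45 | 11.2 / 18.7 | 1.107 | 7.7% |
| | 0.10 | 1.90 | 12.8 / 21.4 | 1.204 | 10.4% |
| Counselor, m = 20 | 0.01 | 1.19 | 10.1 / 16.9 | 1.046 | 6.1% |
| | 0.05 | 1.95 | 13.0 / 21.6 | 1.214 | 10.7% |
| | 0.10 | 2.90 | 15.8 / 26.4 | 1.396 | about 16% |
| Group of 5-8 | 0.05 | 1.20-1.35 | 10.2-10.8 / 17.0-18.0 | 1.049-1.084 | 6.2-7.1% |

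R = 1.107 means the true standard error is 11% larger than the one reported; equivalently, the reported one is 1 − 1/1.107 = 9.7% too small.

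**Step 3: how much the printed 17 points would absorb.** (17/15.5)² is about 1.20. A DE of 1.20 corresponds to an ICC of about 0.02 at m = 10, about 0.01 at m = 20, and about 0.03-0.05 for groups of 5-8.

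**The case against.** **The size is not established.** No ICC is given. The four counselors in F4 belong to the former clinic-based design, and staffing at the new sites is not restated. Groups are optional, so group clustering may be partial. At ICC 0.01 with 10 women per counselor the true error is 5.5%, which is negligible in a pilot. This stands: the direction is supported, the magnitude is conditional. Counselor clustering remains, however, even if no one attends a group.

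**F10 does not exclude a clustered model.** Its wording for the other outcomes leaves the choice open. That is true, but nothing is prespecified, and the one model it names for SRQ-20 has no cluster term.

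**Stronger readings that the documents do not support.**

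- A reader might infer that every test in F10 is invalid. The t-tests and chi-square tests compare baseline characteristics, measured before any counseling, and are unaffected.
- A reader might infer that fidelity comparisons between arms are distorted. F10 lists fidelity among the measures compared across arms, but ESC has no counseling sessions, so there is no ESC contrast.
- A reader might infer that F11 computed 9-17 points from 40 independent women and is therefore too narrow throughout. It does not match that calculation, and its upper end is wide enough for small ICCs by accident of an older sample size.

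**A counselor random intercept is a weak primary model.** With 2-4 counselors it has about 1-3 degrees of freedom (critical t about 12.7 to 3.2), and the ICC would be nearly uninformative. ESC women also have contacts with research assistants (F6), so treating ESC as unclustered is an approximation. Both points stand and shape the fix.

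**It is a pilot.** F11 says effectiveness will be read with caution, and the later trial is to be clinic-randomized, where the clinic-level ICC matters more. This lowers the severity. It does not remove the point, because the arms are still compared.

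**Conclusion.** The point holds for post-randomization outcomes in the 80 individually randomized women. The plan has no allowance for shared counselors or groups in EFB, and any positive ICC makes EFB intervals and EFB-versus-ESC standard errors too small.

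The documents do not determine how large the effect is. At 10 women per counselor it runs from trivial (2% on the standard error at ICC 0.01) to material (20% at ICC 0.10), and it is larger if only two counselors deliver EFB. These figures rest on an assumed ICC, equal caseloads, no clustering in ESC and a normal approximation.

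Separately, the precision ranges in F11 do not match the current sample sizes even under independence, and should be restated in any case. At ICC 0.05 the EFB upper half-width exceeds the printed 17 points in both counselor scenarios.

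Severity is low to moderate: the primary aims are feasibility, acceptability and fidelity, and no confirmatory decision rests on the 5% level.

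**What to change.** 1. **Data.** Record a counselor ID and a postnatal group ID for each EFB woman, and state how many counselors deliver EFB at the two new sites.
2. **F10.** Keep the generalized linear model, with site as a covariate. Beside each between-arm interval, report the interval inflated for EFB-only clustering at ICC 0.01, 0.05 and 0.10, using the actual caseloads. Add, as a sensitivity analysis, a partially nested model with group or counselor as the cluster in EFB and small-sample degrees of freedom. Treat any counselor ICC as descriptive, because counselors are few. State the assumption that ESC contacts with research assistants induce no clustering.
3. **F11.** Replace the within-arm range with 9.3-15.5 points for n = 40 under independence, and give the EFB range with clustering: 11.2-18.7 at ICC 0.05 with 10 women per counselor, 13.0-21.6 with 20. Restate the all-arm range for n = 92 as 6.1-10.2 under independence. Note that acceptability comes from exit interviews in a subset (F9.a), so its precision will be lower.
4. **Fidelity.** Report it per counselor. F9.a samples up to 3 sessions each, so at most 3 × 4 = 12 sessions if there are four counselors.

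The cost is SAP wording and two ID fields. The downside is wider, less favorable intervals and an imprecise ICC.

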- **Training:** counselors serving as counselors from both antenatal and ART clinics will attend a 2-week training. Topics included in the training will be PND, counseling skills, problem solving therapy, and self-care. [name] and members of his team will deliver the training. All training sessions will be audio-recorded for fidelity and assessed using a checklist to ensure the counselors had covered all the critical components.

- **Supervision:** counselors will be supervised and supported by the study's two mental health professionals ([name] and [name]) who will be contacted in the event that a client presents with very high scores on the EPDS or suicidality. A Friendship Bench trainer will provide weekly group supervision for counselors.

F8. Intervention Delivery and Data Collection. Prior to launch, each of the three primary clinics will be randomly assigned to Adapted Friendship Bench (AFB), Enhanced Friendship Bench (EFB) or enhanced standard care (ESC), with the exception of the fourth and fifth clinics which will individually randomize eligible participants to one of the two remaining study arms.

Screening and Enrollment HIV-infected women who are initiating, re-initiating, or continuing ART during pregnancy under the Option B+ will be informed about the study by their provider and invited to participate. Screening and enrollment procedures will take place on the same day as a woman's ANC visit. Women who consent to participate (Appendix 1) will be given an initial screening for perinatal depression or anxiety using the Patient Health Questionnaire (PHQ)-2 and/or the Generalized Anxiety Disorder (GAD)-2 as a part of routine antenatal care. Women who show symptoms perinatal depression or anxiety will be asked to complete the Edinburgh Postnatal Depression Scale (EPDS) and/or the Self-Reporting Questionnaire (SRQ)-20 with a trained psycho-social counselor to confirm symptoms (Appendix 2). Women who screen positively on either the PHQ-2/GAD-2, the EPDS (≥ 10) or SRQ-20 (≥ 8) will be invited to participate. Women screening positive for depression who choose not to participate will be referred to a mental health provider for care.

Study Visits (n=2 for participants in all arms)

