Baseline Visit: At the baseline visit, women will be asked to fill out a questionnaire about their mental health, HIV, and reproductive health history. In addition to assessing depression with the EPDS, we will assess the prevalence of common mental disorders using the Self-Reporting Questionnaire (SRQ-20). The SRQ-20 was designed by the World Health Organization as a screening tool for common mental health disorders (CMD). The SRQ-20 has 20 questions exploring symptoms of depression, anxiety and somatic complaints, rather than a specific diagnosis of depression or anxiety. The SRQ-20 was validated in Malawi and is available in Chichewa.^{50,51} A cut-point of 8 or above has been previously used in Malawi to identify probable CMD. The baseline interview will also assess socio-demographics, self-reported health, and key structural and psychosocial factors including trauma history, intimate partner violence (IPV), other violence in the home, socioeconomic measures, coping, social support, self-efficacy, and experiences of stigma related to HIV and mental health (Appendix 2). Measures of trauma, IPV, and other violence will be important for understanding participants' experience of depression in their broader socioecological context. We have used these measures previously in similar settings.

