6-month Postpartum Visit: At 6 months postpartum, HIV-infected women will be asked to complete the EPDS and SRQ-20 either in-person or by phone. Viral load measures for all HIV-infected women will be collected by study personnel at 6 months postpartum. Information on HIV appointment attendance and infant HIV testing during the first 6 months postpartum will be collected from a participant's medical record, as we are doing in our ongoing USAID project. Information on infant anthropometry (length, weight, head circumference), infant physical health (presence of respiratory illness, diarrhea, and immunization records) and infant development, assessed using the Observation of Mother-Child Interaction (OMCI) guide, the PAMANED Study Family Care Indicators Questionnaire in Chichewa, and the WHO Indicators of Infant and Young Child Development (IYCD) Item guide, which have been validated for use in children as young as 4 months of age, will also be collected (Appendix 2). The OCMI portion of the 6 month postpartum visit will be video-recorded to review the fidelity rating after the visit has occurred. HIV-infected women, counselors and supervisors will be asked to complete a brief exit interview either in-person or by phone to assess the feasibility and acceptability of the intervention.

Counseling Sessions (EFB n= up to 7; ESC, n=0):

Women will be followed from study enrollment at their ANC visit through 6 months postpartum. Women in the

AFB and EFB arms will receive approximately 4 prenatal individual counseling sessions and approximately 2 optional, but recommended postnatal group counseling sessions (n=up to 6 counseling session). Women in the EFB arm will receive up to the same number of counseling sessions (4 prenatal and 2 postnatal) as women in the AFB arm, with an additional social support session described in section F6 (n=up to 7 counseling sessions). Women in the ESC arm will not receive counseling sessions, but will receive psychoeducation from a trained research assistant, referrals as needed, and follow-up calls to assess whether referrals were acted on and whether any further unmet mental health needs remain (n=0 counseling sessions). Counseling sessions will take place every 1-2 weeks at the antenatal care clinic, or via phone, during the prenatal period and approximately monthly during the postnatal period to coincide with routine ART refill visits.

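### F10 gives baseline SRQ-20 no role in the 6-month SRQ-20 score model, which costs precision among the 80 randomised women if the two scores are correlated (low priority)

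*Combined protocol and SAP*

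**What the plan says.** F10 specifies the analysis of the 6-month score in one clause: "statistical models examining differences in SRQ-20 scores at 6 months will be generalized linear models". It gives no covariate, distribution or link. The only use of baseline data that F10 states is a comparison of the arms "using t-tests for continuous variables and chi-square tests for categorical variables to assess balance across study arms".

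SRQ-20 is part of the baseline visit in F8. At 6 months postpartum, F8 says "HIV-infected women will be asked to complete the EPDS and SRQ-20 either in-person or by phone". F9.b uses the baseline score once, in the composite outcome, where remission requires a 50% or greater improvement from baseline together with a score below 8. The other SRQ-20 entry in F9.b is binary: "The proportion of women reporting a score >8".

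On who is compared, F4 says that "only the new 80 women will contribute to between-arm comparisons due to the differences in sites". These women come from "the fourth and fifth clinics which will individually randomize eligible participants to one of the two remaining study arms" (F8), with 40 per arm (F11). F11 asks for cautious reading of effectiveness results. No section mentions covariate adjustment.

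**The concern.** When an outcome score is also measured before randomisation, including the baseline value in the model removes the part of the outcome variance that it predicts. F10 collects that value and then uses it only to test balance. With 40 women per arm, the interval for the arm difference may be wider than the collected data allow.

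The point is limited to the model for the SRQ-20 score. It does not cover the binary SRQ-20 outcome or the composite. Randomisation is individual in this comparison, so validity is not in question. What is at stake is the precision of a preliminary estimate that will be read alongside plans for a larger trial. A named covariate also removes the option of choosing the adjustment after the balance tests have been seen.

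**Working it through.** The plan states no precision, SD, effect size or power for the SRQ-20 comparison, so there is no figure of its own to reproduce. The precision ranges in F11 concern feasibility and acceptability proportions and play no part here.

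**Inputs**
- n = 80, 40 per arm (F4, F11).
- Two-sided alpha 0.05 (F11).
- k = 1 added covariate, baseline SRQ-20.
- r, the correlation of baseline with 6-month SRQ-20 among enrolled women: not in the documents. Assumed range 0 to 0.5.
- Loss to follow-up: no rate is given. Assumed 0%, and 20% (n = 64) as a second case.

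**Standard error.** For a normal model with identity link, the standard error of the arm difference is multiplied by

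factor = sqrt[(1 - r²) × (1 + k/(n - k - 3))].

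The second term is the price of estimating one slope. At n = 80 it is 1 + 1/76 = 1.0132. For example, r = 0.3 gives sqrt(0.91 × 1.0132) = 0.960.

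**Half-width of the 95% interval, in SD units**
- Unadjusted: t(0.975, 78) × sqrt(4/80) = 0.445.
- Adjusted: t(0.975, 77) × sqrt(4/80) × factor.

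**Unadjusted sample size with the same standard error:** 80/factor².

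| r | SE factor | SE change, n = 80 | Half-width (SD) | Equivalent unadjusted n | SE change, n = 64 |
|---|---|---|---|---|---|
| 0 | 1.0066 | +0.7% | 0.448 | 79 | +0.8% |
| 0.2 | 0.9862 | -1.4% | 0.439 | 82 | -1.2% |
| 0.3 | 0.9602 | -4.0% | 0.428 | 87 | -3.8% |
| 0.4 | 0.9225 | -7.7% | 0.411 | 94 | -7.6% |
| 0.5 | 0.8717 | -12.8% | 0.388 | 105 | -12.7% |

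**Break-even.** Setting the factor to 1 gives r² = 1/77, so r = 0.114 at n = 80. At n = 64, r² = 1/61, so r = 0.128.

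**Check on integer, bounded scores.** In 6,000 simulated trials per value of r, with 40 women per arm and no arm effect, baseline scores were rounded and clipped to 8-20 and 6-month scores to 0-20. The mean standard error changed by +0.7%, -1.4%, -4.0%, -7.8% and -12.9% at observed r = 0, 0.2, 0.3, 0.4 and 0.5. The mean arm difference stayed within 0.011 points of zero with and without adjustment. This confirms that the formula holds without normality; it says nothing about which r to expect.

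**Selection at entry.** Enrolling on a positive screen narrows the baseline range and can lower r. As an illustration, keeping the top 30% of a bivariate normal population on baseline reduces r of 0.3, 0.5 and 0.7 to about 0.16, 0.28 and 0.45. Put into the formula at n = 80, these give standard error changes of about -0.7%, -3.5% and -10%. This is not a correction for this trial, because F4, F8 and section J do not state the entry scale consistently.

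**The case against.** The strongest reply is that F10 is silent and does not exclude adjustment. A generalized linear model can take a baseline covariate, so an analyst following F10 could include one. That is true, and it makes this an omission and not an error. But no covariate is named anywhere, and the model as written contains arm only.

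A second reply is that F9.b lists no continuous SRQ-20 outcome, so the F10 clause might refer to the listed proportion. The clause speaks of score differences and is introduced as an addition to the outcomes already covered, which favours the continuous reading.

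Third, the gain depends on the link. In a simulation of 1,500 trials per r with a dichotomised outcome and a logit link, adjustment raised the standard error of the log-odds coefficient by about 2%, 4% and 12% at latent r = 0.2, 0.3 and 0.5, because the coefficient itself then measures something different. That result concerns a binary outcome, which is outside this point. What stands is that the figures above hold for the normal, identity-link model and should not be carried over to another.

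Fourth, the likely gain is at the low end. Entry is on a positive screen, and the two measurements are more than six months apart. This is fair. It reduces the expected benefit but leaves the illustrative values of r above break-even.

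Finally, little turns on the analysis in a feasibility pilot. That is also correct, and it is why the priority is low.

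**Conclusion.** The concern holds, at low priority. F10 gives baseline SRQ-20 no part in the model for the 6-month score, and including it is a better use of data already collected. If r among enrolled women exceeds about 0.11, the standard error falls: by 4.0% at r = 0.3 and 12.8% at r = 0.5. Under the selection illustration the reduction is about 0.7% to 10%. If baseline predicts nothing, the cost is 0.7% (0.8% at n = 64). There is no bias either way.

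The size rests on an assumed r, on the 80 women being individually randomised, and on a normal model with identity link. The main uncertainty is r, which the documents do not give.

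**What to change.** Add to F10:

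> Among the 80 individually randomised women, the 6-month SRQ-20 score will be compared between arms with a generalized linear model (normal family, identity link) that includes arm and baseline SRQ-20 score as a continuous covariate. The adjusted mean difference with its 95% confidence interval will be reported, with the unadjusted difference alongside.

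The normal family and identity link are suggested because they express the result in SRQ-20 points. If another family or link is preferred, name it, keep baseline SRQ-20 in the model, and do not rely on the precision figures given here. A clinic term is optional; include it if randomisation is stratified by clinic, which the documents do not state.

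The cost is one or two sentences and one model term, with no new data. The change should be made before the outcome data are analysed.
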